**Change 16:**

***Section 7.1.2.2 Initial visit-Dose 1, Day 1 (Treatment Arms A, B, and C):***

Moved text and revised:

Old text (paragraph 1, 4th bullet, sub-bullet):

- ~~Hematology results should be reviewed and it should be confirmed that the values are still within the treatment ranges (ANC  $\geq 1.5 \times 10^9/L$ , platelet count  $\geq 100 \times 10^9/L$ , and hemoglobin  $\geq 9.0$  g/dL).~~

New text (paragraph 1, 1st bullet):

- Reconfirmation of eligibility: hematology results obtained within 72 hours of Dose 1, Day 1 should be reviewed and it should be confirmed that the values are still within the treatment ranges (absolute neutrophil count  $\geq 1.5 \times 10^9/L$ , platelet count  $\geq 100 \times 10^9/L$ , and hemoglobin  $\geq 9.0$  g/dL).

**Change 17:**

***Section 5.2.1 Withdrawal:***

Paragraph 1, 6th bullet:

Old text:

- If the subject experiences Grade 3 ~~or~~ 4 neutropenia or thrombocytopenia lasting > 2 weeks despite adequate treatment. Blood transfusions and biologic response modifiers, such as GM-CSF or G-CSF can be used for the treatment of hematological abnormalities during the treatment period

New text:

- If the subject experiences Grade 3 neutropenia or Grades 3 or 4 thrombocytopenia lasting > 2 weeks or Grade 4 neutropenia lasting >7 days despite adequate treatment. Blood transfusions and biologic response modifiers, such as GM-CSF or G-CSF can be used for the treatment of hematological abnormalities during the treatment period

**Section 6.4.7 Dose delays:**

Myelosuppression, 2nd bullet (new 3rd bullet):

Old text:

- If a subject experiences sustained CTCAE Grade 3 ~~or~~ 4 neutropenia or thrombocytopenia (see Table 6-1) lasting > 2 weeks despite adequate treatment, the subject must be discontinued from treatment with radium-223 dichloride.

New text:

- If a subject experiences sustained CTCAE Grade 3 neutropenia or sustained CTCAE Grades 3 or 4 thrombocytopenia (see Table 6-1) lasting > 2 weeks despite adequate treatment, the subject must be discontinued from treatment with radium-223 dichloride.
- If a subject experiences sustained CTCAE Grade 4 neutropenia (see Table 6-1) lasting > 1 week despite adequate treatment, the subject must be discontinued from treatment with radium-223 dichloride.

**Change 18:**

**Section 7.3.4.4 Pain endpoints:**

Old text:

The ~~worst pain score~~ (WPS) is defined for each subject at baseline and at each applicable 4-week assessment date, as the mean of the “worst pain score” values in the last 24 hours from the preceding 7 days before each ~~scheduled~~ visit per the BPI-SF recorded in the subject’s reported outcome pain data.

~~Secondary~~ pain endpoints are defined with respect to the ~~screening period~~ baseline with ~~randomization date~~ as start date, and ~~are~~ based on data collected as of the Week 24 assessment.

Additional details on pain endpoints, including ~~analgesic use~~ details, will be provided in the SAP.

New text:

The WPS is defined for each subject at baseline and at each applicable 4-week assessment date, as the mean of the “worst pain score” values in the last 24 hours from the preceding 7 days before each applicable visit or telephone contact per the BPI-SF recorded in the subject’s reported outcome pain data.

Pain endpoints are defined with respect to each applicable baseline and start date.

The screening baseline for pain endpoints will be based on the pre-Dose 1, 7-day pain assessment.

For purposes of determining pain improvement and pain progression, a daily analgesic use score will be calculated programmatically for each subject for each day, based on the subject's complete CRF data on analgesic use. Analgesic use data will be coded using the WHO drug dictionary. Oral morphine equivalents will be calculated. Each day's analgesic use in OME units will be calculated using the applicable CRF-reported dates and date ranges. The AQA will be applied to obtain a daily analgesic use score. Details will be described in the SAP.

Additional details on pain endpoints, including details on the applicable baselines, evaluability for daily analgesic use increase, calculation of daily analgesic use score(s) applicable to each baseline and post-baseline time point, and definition of baseline values and "increase" in daily analgesic use for purposes of these endpoints, will be provided in the SAP.

#### ***Section 7.3.4.4.1 Pain improvement rate:***

Added text:

Pain improvement is defined for each baseline in subjects evaluable for pain improvement at that baseline, i.e., subjects entering the study with a WPS of at least 4 and evaluable for analgesic use increase at the respective baseline assessment. Pain improvement with respect to each baseline is defined in each applicable evaluable subject at each applicable post-baseline assessment time point as a 30% and 2-point decrease in WPS over 2 consecutive measurements conducted at least 4 weeks apart, without an increase in analgesic use.

Pain improvement rate is defined for each baseline and applicable post-baseline assessment time point as the number of subjects with pain improvement at the time point, divided by the total number of subjects evaluable for pain improvement with respect to the applicable baseline.

#### ***Section 7.3.4.4.2 Time to pain progression:***

Old text:

~~Pain progression is defined in subjects evaluable for pain progression, i.e., subjects entering the study with a WPS of at most 7. A pain progression event consists of an increase of  $\geq 30\%$  and 2 points in WPS over 2 consecutive measurements conducted at least 4 weeks apart, without a decrease in analgesic use, based on the included assessments.~~

The time to pain progression is defined as the time (in days) from ~~randomization date~~ until occurrence of the first pain progression event. Subjects without pain progression as of the last ~~included pain~~ assessment, ~~whether or not surviving~~, will be censored at the ~~last included pain assessment~~.

New text:

Pain progression is defined for each baseline in subjects evaluable for pain progression at the applicable baseline, i.e., subjects with a WPS of  $\leq 7$  at the respective baseline assessment. Pain assessments will occur daily for one week, beginning a week prior to each visit and including the day of the visit. An evaluable pain assessment interval requires completion of a minimum of 4 out of 7 daily questions. Pain progression is defined as the occurrence of either a pain increase or an increase in pain management with respect to the applicable baseline, whichever occurs first.

A pain increase is defined as follows:

- For asymptomatic patients (WPS 0 to  $< 1$  at baseline), pain increase is defined as an increase of 2 or more points in the average (i.e., average of 7-day assessments) “worst pain in 24 hours” score from baseline observed at 2 consecutive evaluations  $\geq 4$  weeks apart
- For mildly symptomatic patients (WPS 1-3 at baseline), pain increase is defined as an increase of 2 or more points in the average (i.e., average of 7-day assessments) “worst pain in 24 hours” score from baseline observed at 2 consecutive evaluations  $\geq 4$  weeks apart and an average worst pain score of  $\geq 4$ ”
- For symptomatic patients with WPS  $> 3$  and  $\leq 7$  at baseline), pain increase is defined as an increase of 2 or more points in the average (i.e., average of 7-day assessments) “worst pain in 24 hours” score from baseline observed at 2 consecutive evaluations  $\geq 4$  weeks apart.

An increase in pain management is defined as follows:

For patients not on opioids at the applicable baseline, initiation of short or long-acting opioid use for pain will constitute an increase in pain management. For patients being treated with  $\leq 600$  OME (oral morphine equivalents) of opioids at the applicable baseline, an increase by 1 point in the daily AQA score and increase  $\geq 50\%$  in daily OMEs will constitute an increase in pain management. For patients being treated at the highest AQA level ( $> 600$  OME/day) at the applicable baseline, an increase  $\geq 50\%$  in daily OMEs from that baseline will constitute an increase in pain management.

The time to pain progression is defined for each applicable baseline for applicable subjects as the time (in days) from the respective baseline until occurrence of the first post-baseline pain progression event. Subjects without pain progression as of the last

applicable post-baseline assessment, whether or not surviving, will be censored at the last applicable post-baseline assessment. Subjects with insufficient applicable baseline assessment(s) or without adequate post-baseline assessment(s) will be censored at the applicable baseline date. Additional censoring and other details will be described in the SAP.

**Change 19:**

***Section 8.4.4 Safety analysis:***

Paragraph 5

Old text:

1. Treatment-emergent safety events

~~This analysis will be performed for safety events observed through the end of treatment visit. For this analysis, subjects will be grouped by treatment arm as treated.~~

3. Safety events emerging following the standard-regimen treatment period

This analysis will be performed in each treatment arm for events following the later of 24 weeks from treatment start or 30 days following completion of 6 doses of radium-223 dichloride treatment. It will be performed for selected safety endpoints collected during active ~~safety~~ follow-up after end of treatment. This analysis will be performed by treatment group as treated.

New text:

1. Treatment-emergent safety events

The treatment period for this study extends from the initiation of treatment until 30 days after the last administration of radium-223 dichloride. Events starting or worsening within the treatment period will be considered treatment-emergent.

For the analysis of treatment-emergent safety events, subjects will be grouped by treatment arm as treated.

3. Safety events emerging following the standard-regimen treatment period

This analysis will be performed in each treatment arm for events following the later of 24 weeks from treatment start or 30 days following completion of 6 doses of radium-223 dichloride treatment. It will be performed for selected safety endpoints collected during active follow-up after end of treatment

through primary endpoint completion. This analysis will be performed by treatment group as treated.

4. Safety events emerging during long-term follow-up following primary endpoint completion

Safety events emerging following primary endpoint completion and any events emerging during long-term follow-up, will be reported in a separate document(s) from the study Clinical Study Report.

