**Section 7.1.2.6.1 Active follow-up with clinic visits:**

Paragraph 3, 1st sentence:

Added text:

The following assessments will be performed during the clinic visits:

Paragraph 9:

Added text:

If a subject is no longer able to travel to the clinic due to deteriorating status, the subject will enter the active follow-up without visits and will be followed by telephone.

Paragraph 10:

Old text:

If a subject has a SSE in the active ~~safety~~-follow-up period, he will continue the ~~2-year~~ active ~~safety~~ follow-up period.

New text:

If a subject has an SSE in the active follow-up period, he will continue the active follow-up period for 2 years from last study treatment. If a subject becomes unable to travel to the clinic after 2 years after his last treatment, he will enter long-term follow-up.

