### ***Section 8.4.4 Safety analysis:***

Paragraph 5, 3rd subsection:

Added text:

3. Safety events emerging following the standard-regimen treatment period

This analysis will be performed in each treatment arm for events following the later of 24 weeks from treatment start or 30 days following completion of 6 doses of radium 223 dichloride treatment. It will be performed for selected safety endpoints collected during active follow-up after end of treatment through primary endpoint completion. This analysis will be performed by treatment group as treated.

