during the active follow-up with clinic visits period. Contrast agents will only be captured as concomitant medication if there is an AE or SAE related to administration of contrast media.

- ee. Subjects who receive further anticancer therapy during the active follow-up period will have an end of active follow-up with clinic visits and will enter the active follow-up without clinic visits (telephone follow-up). Subjects who receive further anticancer therapy after 2 years from last study treatment will enter long-term follow-up.
- ff. All AEs and SAEs will be assessed and recorded from the time the ICF is signed until 30 days after the last dose of study medication. All AEs should be assessed and documented prior to each dose of radium-223 dichloride.
- gg. Any AEs and SAEs occurring beyond 30 days after the last treatment must be documented and reported if considered to be related to study medication or if related to an SSE. However, all occurrences of leukemia, myelodysplastic syndrome, aplastic anemia, and primary bone cancer or any other new primary malignancy must be reported as SAEs at any time and regardless of the investigator's causality assessment.
- hh. Any SAEs must be documented and reported if considered to be related to study medication. However, all occurrences of leukemia, myelodysplastic syndrome, aplastic anemia, and primary bone cancer or any other new primary malignancy must be reported as SAEs at any time and regardless of the investigator's causality assessment.

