#### New text:

All study subjects will be eligible for further follow-up either in this study or in a separate long-term follow-up study for up to 7 years. The separate long-term follow-up study has been set up to follow subjects who received radium-223 dichloride or placebo in the course of Bayer-sponsored clinical trials. The long-term follow-up study has a specific focus on investigator reported, radium-223 dichloride-related AEs and SAEs, hematologic toxicity (e.g., myelosuppression / myelofibrosis / bone marrow aplasia), new primary malignancies including leukemias and solid tumors, and survival for up to 7 years after last dose of radium-223 dichloride or until death. During long-term follow-up, subjects will be contacted every 6 months by telephone. All subjects who transition into this separate long-term follow-up study will require a separate signed informed consent.

Transition of all subjects into the separate long-term follow-up study will begin following the later of primary endpoint completion or 2 years after the last radium-223 dichloride treatment is administered to the last treated subject.

Until the transition to the long term follow-up study begins, some subjects may begin long-term follow-up in this study. This study will end when all subjects have transitioned into the long-term follow-up study or discontinued from this study for another reason (e.g., Consent Withdrawn, Lost to Follow-up).

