#### 13.4.1.2 Change 2:

Bone fractures and bone associated events (e.g., osteoporosis) need to be reported as (S)AEs, including during long-term follow-up, regardless of causality to study treatment.

Sections affected include:

- Synopsis - Methodology
- 4.1 Design overview
- 6.8 Post-study therapy
- 7.1.1 Tabulated overview
- 7.1.2.7.1 Active follow-up with clinic visits
- 7.1.2.7.2 Active follow-up without scheduled clinic visits
- 7.1.2.8.1 End of active follow-up with clinic visits
- 7.1.2.8.2 End of active follow-up without scheduled clinic visits

- 7.1.2.9 Long-term follow-up to 7 years following last dose
- 7.1.2.9.1 Long-term follow-up (via telephone follow-up)
- 7.1.2.9.2 End of long-term follow-up
- 7.5.1.3 Assessments and documentation of adverse events
- 7.5.1.4 Reporting of serious adverse events
- 10 Premature termination of the study

*Rationale:* The ERA 223 study, a phase III randomized trial in prostate cancer patients examining radium-223 dichloride versus placebo in combination with abiraterone and prednisone (study number 15396, NCT02043678) was unblinded based on the IDMC recommendation following an ad hoc independent analysis where more treatment emergent fractures, SSE-FS, and total deaths events were observed in the active treatment arm compared with the placebo arm. Based on these data European Health Authorities requested that all bone fractures and bone associated events (e.g., osteoporosis) occurring during study and in the follow-up period should be documented regardless of causality to study treatment.

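### Section 8.4.4 item 4 contradicts its own heading and leaves long-term follow-up events that occur before the primary cut-off out of every study-report analysis shown

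*Protocol*

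**What the plan says.** The text is the new wording of Section 8.4.4 in Amendment 1, Change 19. Item 3 covers events after the standard-regimen period: "It will be performed for selected safety endpoints collected during active follow-up after end of treatment through primary endpoint completion". Item 4 is headed "Safety events emerging during long-term follow-up following primary endpoint completion". Its body names two groups for separate reporting, the second with no date condition: events after primary endpoint completion "and any events emerging during long-term follow-up, will be reported in a separate document(s) from the study Clinical Study Report".

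The protocol expects some subjects to be in long-term follow-up early. Amendment 2, Change 10 (Section 4.1 and parallel sections) starts the transfer to the separate long-term study no earlier than primary endpoint completion, and adds: "Until the transition to the long term follow-up study begins, some subjects may begin long-term follow-up in this study". The routes are:

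- Subjects with an SSE stay in active follow-up for 2 years from last treatment (Section 7.1.2.6.1 in Amendment 1; Table 7-1, footnote cc).
- Telephone-only follow-up lasts 2 years (Section 7.1.2.7.2 in Amendment 2).
- Loss of ability to travel: "If a subject becomes unable to travel to the clinic after 2 years after his last treatment, he will enter long-term follow-up" (Section 7.1.2.6.1).
- New therapy: "Subjects who receive further anticancer therapy after 2 years from last study treatment will enter long-term follow-up" (Table 7-1, footnote ee).

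Drug-related AEs and SAEs, marrow disorders and new primary malignancies are recorded in long-term follow-up (Section 7.1.2.9.1, Amendment 3). Amendment 4, Change 2 adds: "Bone fractures and bone associated events (e.g., osteoporosis) need to be reported as (S)AEs, including during long-term follow-up, regardless of causality to study treatment".

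**The concern.** If the body of item 4 is followed, the same event on the same calendar day is inside or outside the study report depending only on which follow-up period the subject is in. The events concerned are the late harms for which 7-year follow-up was set up. They include the fractures that Amendment 4 asked to be documented after another radium-223 trial showed more of them. The report's counts of these events would not be complete to one common date. Because the 2-year clock starts at the last dose, the point from which events can be excluded also differs between the 6-dose arms and the 12-dose arm when counted from Dose 1.

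**Working it through.** **1. Scope of the items.** The first group in the body of item 4 already contains every long-term follow-up event after the cut-off. The second clause therefore adds something only for long-term follow-up events before the cut-off, which the heading of the item does not cover. Heading and body disagree. Item 3 does not pick these events up, because it is confined to active follow-up. Item 1 stops 30 days after the last dose. Item 2 is not in the part shown.

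**2. The plan's own figures.** Section 8.6 (Amendment 1, Change 10) gives an average of 39 months to the cut-off. This cannot be reproduced, because the accrual period is not in the part shown. The Comparison 2 power stated with it can: Φ(√(74.9 × 0.25) × |ln 0.606| − 1.2816) = Φ(2.167 − 1.282) = 81.2%, against the stated 80.6%.

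**3. Earliest entry under the 2-year rules.** Last scheduled doses are Week 20 (Arms A and B) and Week 44 (Arm C), from Table 7-1. Two years = 104.36 weeks; 1 week = 7/30.4375 months.

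| | Arms A/B | Arm C |
|---|---|---|
| Last dose + 2 years | 20 + 104.36 = Week 124.4 | 44 + 104.36 = Week 148.4 |
| In months from Dose 1 | 28.6 | 34.1 |
| Longest time before month 39 | 39 − 28.6 = 10.4 | 39 − 34.1 = 4.9 |

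Taking 2 years as 104 weeks gives 28.5 and 34.0 months. The last row applies to the first subjects enrolled and takes the 39 months from the first subject's Dose 1 (assumption). Amendment 2 allows up to 28 days from randomization to Dose 1, so counting from randomization shortens both windows by up to 0.9 month.

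**4. Arm difference.** For full courses it is 44 − 20 = 24 weeks. It is smaller with early stopping. Assume that dosing stops only at the plan's own event-or-loss rates:

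- SSE-FS hazard, standard dose: ln 2/9 = 0.0770 per month.
- Total hazard to Week 24 (5.52 months): −ln(0.5535)/5.52 = 0.1072, so loss = 0.1072 − 0.0770 = 0.0301 (from unrounded values).
- Total hazard in Arm C after Week 24: 0.606 × 0.0770 + 0.0301 = 0.0768.

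Mean last dose = 4 weeks × the sum of the probabilities of still being on treatment at each dose after the first. This gives Week 15.0 in Arm A and Week 26.2 in Arm C, a gap of 11.2 weeks. An Arm C subject who stops at or before Dose 6 contributes no gap.

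**5. How many could be affected.** This cannot be derived. A ceiling is the share of entry dates early enough to allow it, 10.4/R or 4.9/R for uniform accrual over R months (assumption):

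| R (months) | Arms A/B | Arm C |
|---|---|---|
| 12 | 87% | 41% |
| 21.7 | 48% | 22% |
| 28 | 37% | 17% |

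The middle row is the accrual length at which the hazards in step 4 give 74.9 Comparison 2 events at month 39. All rows ignore deaths and count SSE-free subjects who are still in active follow-up, so true shares are lower by an unknown amount.

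**The case against.** Five arguments weigh against the point.

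- **The heading governs.** If item 4 covers only long-term follow-up after primary endpoint completion, nothing is lost. That is one possible reading, but it leaves the second clause of the body with no function. A programmer working from the body would exclude the events.
- **The affected group may be empty or smaller.** Section 6.8 (Amendment 1, Change 12) keeps active follow-up open to the later of 2 years or maturity of the primary analysis, which would leave nobody in long-term follow-up before the cut-off. Section 4.1 (Amendment 2) lets active follow-up without visits run to an SSE, death, loss or withdrawal, with a 7-year maximum. Both conflict with the 2-year rules listed above. This limits any claim about size.
- **The arm difference depends on the clock.** For subjects who leave at 2 years, the window after the last dose is the same in all arms. A common calendar cut-off gives Arms A and B the longer window after the last dose. This stands: the choice of clock can be left to the SAP.
- **Nothing is lost outright.** The events are still reported, in a separate document, and most of a 7-year follow-up falls after month 39 under any wording. This stands too.
- **The current Section 8.4.4 is not in the part shown.** Amendment 2 lists only treatment-period and dose-notation changes there, and Amendments 3 and 4 do not list the section. The wording is probably current, but this is unconfirmed.

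A reader might infer that the plan builds in a 24-week bias against extended dosing, or that most Arm A and B subjects lose late events. The documents do not support either. Twenty-four weeks is the full-course maximum, entry is not automatic at 2 years (SSE-free subjects attending clinic stay in active follow-up), and the large shares rest on an assumed short accrual before deaths.

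**Conclusion.** The point holds as an internal contradiction with a real but unquantified consequence. Heading and body of item 4 disagree. On the body text, new malignancies, marrow disorders, fractures and drug-related SAEs in long-term follow-up before the cut-off fall in no study-report analysis shown.

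Under the 2-year rules this can begin 10.4 months before the expected cut-off in Arms A and B and 4.9 months before it in Arm C, for the earliest full-course subjects. The arm difference from Dose 1 is at most 24 weeks, about 11 weeks on average under the attrition assumption. Only subjects alive and in long-term follow-up before the cut-off are concerned. The conclusion rests on the Amendment 1 wording still being in force and on the 2-year rules applying rather than Section 6.8. No power or sample size figure is affected.

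**What to change.** In item 4, delete the clause on any events emerging during long-term follow-up and align the heading, so that only events with onset after the primary endpoint data cut-off are reported separately. In item 3, for the event types collected in both periods (new primary malignancies, leukaemia, myelodysplastic syndrome, aplastic anaemia, fractures and bone-associated events, drug-related SAEs), include every event with onset up to the cut-off, whichever follow-up period the subject is in.

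Separately, reconcile the statements on how long active follow-up lasts: Section 6.8 and the Amendment 2 text of Section 4.1, against the Synopsis and Section 4.1 text of Amendment 1 and the sections on active follow-up with and without clinic visits.

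The cost is two sentences in Section 8.4.4 and one date-based filter in the safety programs. The data are already collected. The downside is that long-term telephone data up to the cut-off must be cleaned in time for the study report.
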